6.3 Radiation Dose Adjustments

Radiation therapy will be held for Grade 3 or 4 nausea that is not well controlled with anti-emetic support, until nausea resolves to Grade 2 or less. It will then be resumed to complete the remaining radiation therapy course after multi-disciplinary discussion and at the discretion of the treating physicians.

6.4 Capecitabine Dose Adjustments

Capecitabine dose modifications are at the discretion of the treating physician following the guidelines outlined in the package insert. Toxicity due to capecitabine administration may be managed by symptomatic treatment, dose interruptions and adjustment of capecitabine dose. Once the dose has been reduced it should not be increased at a later time.

6.4 5-Fluorouracil continuous infusion (CI) Dose Adjustments

5-FU CI dose modifications are at the discretion of the treating physician following the guidelines outlined in the package insert. Toxicity due to infusional 5-FU administration may be managed by symptomatic treatment, dose interruptions and adjustment of infusional 5-FU dose.

Once the dose has been reduced it should not be increased at a later time.

7. ADVERSE EVENTS: LIST AND REPORTING REQUIREMENTS

Adverse event (AE) monitoring and reporting is a routine part of every clinical trial. The following list of reported and/or potential AEs (Section 7.1) and the characteristics of an observed AE (Section 7.2) will determine whether the event requires expedited reporting **in addition** to routine reporting.

7.1 Expected Toxicities

7.1.1 Adverse Event List(s) for NIS793

Less Common (less than 5 in 100)

- Allergic reaction
- Cytokine release syndrome
- Cardiac toxicity such as valvulopathy
- Skin rash
- Bleeding or bruising
- Lowering of blood counts
- Decreased kidney function
- Eye pain, visual disturbances, and color perception changes
- Liver test abnormalities
- Bone pain
- Fatigue
- Specific skin issues including keratoacanthomas and squamous cell carcinoma

7.1.2 Adverse Event List(s) for mFOLFIRINOX (Fluorouracil, leucovorin, oxaliplatin, irinotecan)

7.1.2.1 5-Fluorouracil:

Very Common (more than 1 in 10 patients)

- Sickness
- Vomiting
- Mouth sores
- Diarrhea
- Abdominal pain
- Tiredness
- Swelling and redness of the skin
- Fever

Less Common (less than 5 in 100)

- Itching, peeling, and/or pain of the skin of the hands and feet (hand-foot syndrome)
- Diminished appetite
- Loss of hair
- Dizziness
- Cardiac disorders such as angina
- Heart attack and change of heart rhythm
- Confusion
- Disorientation
- Emotional instability
- Watering of the eyes due to excessive tear production
- Abnormal drowsiness
- Weakness
- The lowering of blood cells
- Bleeding or bruising

7.1.2.2 Leucovorin:

Less Common (less than 5 in 100 patients)

- Allergic reaction
- Rash
- Itching
- Facial flushing

- Nausea
- Vomiting

7.1.2.3 Irinotecan:

Very Common (more than 1 in 10 patients)

- A decrease in blood counts (red blood cells, white blood cells, and platelets)
- Anorexia
- Mild Diarrhea
- Mild fatigue
- Sores in the mouth and throat (mucositis)
- Cardiovascular events such as a fast or irregular heartbeat
- Hair loss
- Abnormal liver test values
- Decreased kidney function
- Nausea and vomiting
- Constipation
- Pain

Less Common (less than 5 in 100 patients)

- Severe Diarrhea
- Hemorrhage which may require a blood transfusion
- Moderate fatigue
- Infection

Rare but Serious

- A serious decrease in blood counts that could result in infection, sepsis, a need for blood transfusion, a need for platelet replenishment
- Liver failure that may lead to death
- Kidney failure that may lead to death or the need for dialysis
- Heart attack
- Stroke

- Hypertension

7.1.2.3 Oxaliplatin:

Very Common (more than 1 in 10 patients)

- Peripheral sensory neuropathy, especially in the case of cold exposure, and an unusual feeling of numbness of the mouth and throat that may cause difficulty in swallowing, and can be made worse by cold water or drinks
- This neuropathy can cause the following:
 - o Acute reversible, primarily peripheral, sensory neuropathy that is of early onset, occurring within hours or one to two days of dosing, that resolves within 14 days, and that frequently recurs with further dosing. This is a sensation of pain when you are exposed to cold, either by touch, or by eating/drinking something cold. Do not eat or drink anything that is colder than room temperature for five days after you receive each dose of oxaliplatin.
 - o Decrease in feeling or funny feeling in the hands, feet and mouth or throat that can interfere with daily activities (writing, buttoning, swallowing, and walking). This may worsen over time.
- Jaw spasm
- Abnormal tongue sensation
- Difficulty speaking
- Eye pain
- Feeling of chest pressure
- Fatigue
- Nausea
- Vomiting
- Diarrhea

Less Common (less than 5 in 100 patients)

- Mouth sores
- Hair loss
- Temporary loss of hearing

- Disturbances of kidney function
- Reduced reflexes
- Skin rash
- Fever
- Fainting
- Fibrosis of the lung
- Severe allergic reaction and mild to moderate swelling and redness at the injection site
- An acute syndrome of pharyngolaryngeal dysesthesia seen in 1-2% of patients that is characterized by a feeling of tightness or tingling in the throat.
- The lowering of blood cell counts
- Bleeding or bruising
- Increase in the value of liver enzymes

7.1.3 Adverse Event List for Capecitabine

Very Common (more than 1 in 10 patients)

- Edema
- Fatigue
- Palmar-plantar erythrodysesthesia (hand-and-foot syndrome)
- Dermatitis.
- Diarrhea
- Nausea, vomiting
- Abdominal pain
- Stomatitis
- Decreased appetite
- Lowering of white blood cell counts
- Anemia
- Thrombocytopenia
- Increase in Bilirubin
- Elevation of liver tests
- Paresthesia

- Eye irritation
- Dyspnea

Less Common (less than 5 in 100 patients)

- Venous thrombosis
- Chest pain
- Headache
- Lethargy
- Dizziness
- Insomnia
- Mood alteration, depression.
- Nail disorder
- Rash
- Skin discoloration
- Alopecia
- Erythema.
- Dehydration
- Gastrointestinal motility disorders
- Oral discomfort
- Taste perversion
- Dyspepsia
- Gastrointestinal hemorrhage
- Ileus
- Neuromuscular & skeletal: Back pain, weakness, neuropathy, myalgia, arthralgia, limb pain
- Abnormal vision
- Conjunctivitis
- Cough

7.1.4 Events expected after radiation

Very likely (80-90%)

- Fatigue (which generally goes away after the radiation therapy is completed)
- Temporary changes in blood work (decrease in blood counts, increase in liver enzymes), without symptoms

Less likely (30%)

- Nausea, vomiting (during therapy) – more common if stomach or gastrointestinal track irradiated
- Skin irritation, redness, itchiness, discomfort

Less likely, but serious (<5%)

- Gastric, esophagus, small bowel or large bowel irritation/ulceration, bleeding, fistula, obstruction or changes in motility following therapy (may require medications or surgery) (< 5% permanent changes)
- Radiation-induced liver disease (RILD) (<1%). Classic RILD is a clinical diagnosis of anicteric ascites, hepatomegaly and elevation of alkaline phosphatase relative to other transaminases that may occur 2 weeks to 3 months following radiation to the liver
- Non-classic RILD includes elevation of liver enzymes and/or any decline in liver function within 12 weeks from start of therapy (~5%). RILD can lead to liver failure that could lead to death. There is an increased risk of liver toxicity in patients with large tumors and in patients with pre-existing liver disease.
- Permanent thrombocytopenia (<1%); this may lead to bleeding
- Kidney injury (<1%); this may lead to changes on imaging and more rarely the need for medication.
- Diabetes (<1%)
- Cancer caused by radiation (<0.1%)

7.2 Adverse Event Characteristics

CTCAE term (AE description) and grade: The descriptions and grading scales found in the revised NCI Common Terminology Criteria for Adverse Events (CTCAE) version 5.0 will be utilized for AE reporting. All appropriate treatment areas should have access to a copy of the CTCAE version 5.0. A copy of the CTCAE version 5.0 can be downloaded from the CTEP web site http://ctep.cancer.gov/protocolDevelopment/electronic_applications/ctc.htm.

For expedited reporting purposes only:

- AEs for the agent(s) that are listed above should be reported only if the adverse event varies in nature, intensity or frequency from the expected toxicity information which is provided.
- Other AEs for the protocol that do not require expedited reporting are outlined in the next section (Expedited Adverse Event Reporting) under the sub-heading of Protocol-Specific Expedited Adverse Event Reporting Exclusions.

Attribution of the AE:

- Definite – The AE *is clearly related* to the study treatment.
- Probable – The AE *is likely related* to the study treatment.
- Possible – The AE *may be related* to the study treatment.
- Unlikely – The AE *is doubtfully related* to the study treatment.
- Unrelated – The AE *is clearly NOT related* to the study treatment.

7.3 Adverse Event Reporting

7.3.1 In the event of an unanticipated problem or life-threatening complications treating investigators must immediately notify the PI.

7.3.2 Investigators **must** report to the PI any adverse event (AE) that occurs after the initial dose of study treatment, during treatment, or within 30 days of the last dose of treatment on the local institutional SAE form.

7.3.3 Adverse Event Reporting Guidelines

All participating sites will report AEs to the Sponsor-Investigator per DF/HCC requirements, and the IRB of record for each site as applicable per IRB policies. The table below indicates which events must be reported to the DF/HCC Sponsor-Investigator.

Attribution	DF/HCC Reportable Adverse Events(AEs)				
	Gr. 2 & 3 AE Expected	Gr. 2 & 3 AE Unexpected	Gr. 4 AE Expected	Gr. 4 AE Unexpected	Gr. 5 AE Expected or Unexpected
Unrelated Unlikely	Not required	Not required	5 calendar days [#]	5 calendar days	24 hours*
Possible Probable Definite	Not required	5 calendar days	5 calendar days [#]	5 calendar days	24 hours*
# If listed in protocol as expected and not requiring expedited reporting, event does not need to be reported.					
* For participants enrolled and actively participating in the study or for AEs occurring within 30 days of the last intervention, events must be reported within 1 business day of learning of the event.					

7.3.4 Protocol-Specific Adverse Event Reporting Exclusions

For this protocol only, all AEs are to be captured and reported to the sponsor-investigator.

7.4 **Reporting to the Food and Drug Administration (FDA)**

The Sponsor-Investigator will be responsible for all communications with the FDA. The Sponsor-Investigator will report to the FDA, regardless of the site of occurrence, any serious adverse event that meets the FDA's criteria for expedited reporting following the reporting requirements and timelines set by the FDA.

7.5 **Reporting to Hospital Risk Management**

Participating investigators will report to their local Risk Management office any participant safety reports, sentinel events or unanticipated problems that require reporting per institutional policy.

7.6 Routine Adverse Event Reporting

All Adverse Events **must** be reported in routine study data submissions to the PI on the toxicity case report forms. **AEs reported through expedited processes (e.g., reported to the IRB, FDA, etc.) must also be reported in routine study data submissions.**

8. PHARMACEUTICAL INFORMATION

A list of the adverse events and potential risks associated with the investigational and other agents administered in this study can be found in Section 7.1.

8.1 NIS793

8.1.1 Description

NIS793 is a fully human anti-TGF β IgG2 mAb that belongs to the IgG2/λ isotype subclass and binds TGF β 1 and TGF β 2 with high affinity and, to a lesser extent, TGF β 3. It is expressed in a Chinese hamster ovary cell line (CHO-C8TD) and consists of two heavy chains and two light chains. The theoretical average molecular mass of NIS793 based on the amino acid composition as deduced from the DNA sequence without post-translational modification is 143,519 Daltons. The drug substance is a slightly to strongly opalescent, colorless to slightly yellowish aqueous solution.

Following administration of NIS793 via a 30 minute intravenous infusion, approximately dose-proportional increase in NIS793 exposure (i.e. Cycle 1 C_{max} and AUClast) was observed from 0.3 mg/kg to 30 mg/kg. Moderate accumulation (approximately up to 2.0-fold) of NIS793 was observed based on ratio of AUClast and C_{max} on cycle 3 versus cycle 1. PK variability was low to moderate as illustrated by between subject variability [coefficient of variation % (CV%)] (e.g. 12.9 to 73.3 % for C_{max}).

Population PK analysis on the concentration data from the dose escalation phase of the study

CNIS793X2101 was used to describe the pharmacokinetic characteristics of NIS793 including the impact of weight as a covariate on clearance and volume of distribution. The analysis suggested that the pharmacokinetics of NIS793 can be well described using a two compartment model with first order elimination from the central compartment. This is consistent with the observation that NIS793 PK appears dose proportional and time-independent based on the non-compartmental analyses. Based on preliminary population PK analysis, the estimated terminal half-life is approximately 18 days (95% confidence interval: 9 to 30 day), the systemic clearance is 9 mL/h with inter-individual variability of 31% and the volume of distribution at steady state is 5.1 L, consistent with the values for conventional monoclonal antibody. There was no significant difference in PK observed among various tumor types. Although body weight (BW) is a covariate on clearance in the population PK model with the estimated exponent of 0.55 (CV% = 40%) from the power model, the predicted exposure and trough concentration at steady state between weight-based and fixed dosing regimens were comparable across different BW categories. This analysis supports the use of fixed or flat dosing on a mg basis irrespective of patient body weight as weight-based dosing does not decrease inter-individual variability. Model-based simulations indicated that a dose of 2100 mg would match exposure observed at 30 mg/kg.

Renal elimination is relatively unimportant for mAbs as their large size limits the extent of their glomerular filtration. The majority of mAb elimination occurs via intracellular catabolism. Therefore, no specific studies were conducted to study NIS793 excretion or elimination.

No specific drug–drug interactions studies were conducted for NIS793. NIS793 is a mAb, not metabolized by Cytochrome P450 (CYP450) enzymes, or transported by P-glycoprotein (Pgp) or related ABC membrane transporters.

8.1.2 Form

NIS793 liquid concentrate for solution for infusion is provided in glass vials with rubber stoppers which are sealed with a flip-off caps. Each 10 mL glass vial contains 700mg/7mL of NIS793 liquid concentrate. A 7% overfill is provided to allow a complete withdrawal of the entire dose. The formulation does not contain a preservative as it is to be used for single-dose administration

only. In the future, 15 mL glass vials containing 1050 mg/mL NIS liquid concentrate may be used.

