5 TREATMENT PLAN

5.1. Treatment Regimen

The defined trial treatment to be used in this trial is outlined below in Table 2. Patients will be randomized 2:1 to Arms A and B, the combination of mFOLFIRINOX with NIS793 and mFOLFIRINOX, respectively. Arm A will accrue 30 patients and arm B will accrue a total of 15 patients. Treatment with NIS793 will not be blinded.

Table 2. Trial treatment

Regimen Description					
Arm	Fluorouracil (mg/m ² IV on days 1 over 46 hours of a 14-day cycle)	Leucovorin (mg/m ² IV on days 1 of a 14-day cycle)	Irinotecan (mg/m ² IV on days 1 of a 14-day cycle)	Oxaliplatin (mg/m ² IV on days 1 of a 14-day cycle)	NIS793 (mg/m ² IV on days 1 of a 14-day cycle)
A	2400 mg/m ²	400 mg/m ²	150 mg/m ²	85 mg/m ²	2100mg
B	2400 mg/m ²	400 mg/m ²	150 mg/m ²	85 mg/m ² .	

Appropriate dose modifications are described in Section 6. Reported adverse events and potential risks are described in Section 7. No investigational or commercial agents or therapies other than those described below may be administered with the intent to treat the participant's malignancy.

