5.3 Agent Administration

5.3.1 IND Agent: NIS793

NIS793 will be administered at a fixed dose of 2100mg via IV infusion every 14 days +3/-1 days, before administration of FOLFIRINOX.

NIS793 will be supplied in a vial as liquid concentrate for infusion. At the appropriate time, infuse the volume of the infusion bag with a maximum administration time of 60 minutes. Shorter infusion times can be applied with a minimum infusion time of 30 minutes. The selection of infusion speed within that requirement is the responsibility of the project-responsible clinician and needs to comply with the specs given by the pump. Infusion must take place in a facility with appropriate resuscitation equipment available at the bedside, and a physician readily available during the period of drug administration.

Per sponsor, Baxter: Long primary flush tubing with 0.2 micron filter extension set add-on (PVC-containing) (for volumes \leq 150 ml) 2R8537 + 1C8363 are acceptable to be used. In addition, needles with a length of 2" or longer are recommended as a standard dimension, which was also used in Technical Research and Development (TRD) compatibility studies with NIS793. Shorter needles may be used as long as correct dosing is assured. In terms of needle diameter, gauge numbers equal to or larger than 21G are recommended, so 22 or 23G needles are fine as well.

Participants should be closely observed for potential infusion-related reactions including rigors, chills, wheezing, pruritus, flushing, rash, hypotension, hypoxemia, and fever, and vital signs monitored more frequently if clinically indicated, during and for at least 2 hours after the first two NIS793 infusions. No pre-medications are to be administered during the observation window. The same may apply for the subsequent NIS793 infusions if medically indicated. Participants should notify study personnel if symptoms of infusion reaction occur after any NIS793 infusion. Further instructions for the preparation and dispensation of NIS793 are described in the study pharmacy manual.

Management and dose modifications associated with the administration of NI793 are outlined in Section 6.

Other Agent(s)

5.3.2 mFOLFIRINOX

All participants on both arms will receive mFOLFIRINOX, consisting of 5-Fluorouracil (5-FU), Oxaliplatin, Irinotecan, and Leucovorin. These drugs are commercially available. A central line will be placed for these infusions.

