Given that mFOLFIRINOX is standard of care, study treatment will be continued as per institutional standard of care.

No pre-medications for mFOLFIRINOX are to be administered during the NIS793 observation window.

The FOLFIRINOX regimen will be administered intravenously. Treatment will be every 14 days +3/-1 days at physician discretion (unless a further delay is mandated by toxicity criteria). There will be eight cycles of FOLFIRINOX, with each cycle being 14 days in length. Treatment will be administered on an *outpatient* basis. Participants enrolled on Arm A will be treated with mFOLFIRINOX chemotherapy as per institutional standards with NIS793 at 2100mg IV every 2 weeks. Participants enrolled on Arm B will be treated with mFOLFIRINOX chemotherapy alone as per institutional standards.

Dosing schedules and modifications: all commercially supplied drugs will follow the manufacturer-provided labeling with respect to its storage and stability, preparation, handling, and administration. Decisions regarding dose modifications, and delays will be made for each patient at the discretion of the attending physician. All other treatments, including chemotherapy pre-medications, will be determined at the discretion of the attending physician.

All treatments, anti-emetics, and supportive medications should follow institutional guidelines. Subcutaneous growth factor support will be administered between 0 and 72 hours after

discontinuation of continuous infusion of 5-FU in all patients receiving FOLFIRINOX after each cycle. Participants may self-administer at home or have the injection administered in clinic.

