8.1.4 Compatibility

This study will use 700mg/7mL NIS793 liquid concentrate. There is a new 1050mg/10.5mL formulation which may be used in the future. Detailed information on the reconstitution of the dosage form is available in the ‘Pharmacy Manual’.

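### NIS793 units are inconsistent in two places: the Table 2 column heading (mg/m² over a 2100 mg cell) and the strength of a possible future vial (1050 mg/mL against 100 mg/mL)

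*Combined protocol and SAP*

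**What the plan says.** **Unit of dose.** Section 5.1 presents Table 2 as the definition of trial treatment. The NIS793 column is headed "NIS793 (mg/m ² IV on days 1 of a 14-day cycle", and the Arm A cell beneath it reads 2100 mg. Section 5.3.1 states: "NIS793 will be administered at a fixed dose of 2100mg via IV infusion every 14 days". Section 5.3.2 describes Arm A chemotherapy "with NIS793 at 2100mg IV every 2 weeks". The pharmacokinetic text in section 8.1.1 supports flat dosing in mg, and footnote C of the study calendar (section 10) gives 2100 mg. The calendar's double-asterisk footnote is attached to the column for day 1 of each chemotherapy cycle. It has drug doses changed when weight or body surface area changes, under institutional criteria or, failing those, a 10% rule. NIS793 is given in that column, and the footnote does not exempt it.

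**Vial strength.** For the current product, section 8.1.2 states: "Each 10 mL glass vial contains 700mg/7mL of NIS793 liquid concentrate". Section 8.1.4 agrees: "This study will use 700mg/7mL NIS793 liquid concentrate". For a possible later product, section 8.1.2 states: "In the future, 15 mL glass vials containing 1050 mg/mL NIS liquid concentrate may be used". Section 8.1.4 states: "There is a new 1050mg/10.5mL formulation which may be used in the future". Both 8.1.4 and 8.1.7 send the reader to the Pharmacy Manual for preparation.

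**The concern.** The unit of dose and the vial strength are what a person building an order set or preparing an infusion looks up.

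Table 2 is the natural source for an order set, and its heading and cell do not carry the same unit. A reader who takes the heading at face value could find apparent support in the calendar footnote on body surface area.

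The two descriptions of the future vial cannot both be true of one product, because they imply very different volumes for the same amount of drug.

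An error from either source would change exposure in Arm A, which has 30 planned patients and a five-patient safety lead-in. Section 2.2 says that NIS793 has not yet been combined with FOLFIRINOX or radiation in clinical trials.

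**Working it through.** This is unit arithmetic. Concentration is mg divided by mL, volume is dose divided by concentration, and a surface-area dose is mg/m² multiplied by body surface area.

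**Vial strength**

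| Source | Statement | Concentration |
|---|---|---|
| 8.1.2 and 8.1.4, vial in use | 700 mg in 7 mL | 700 / 7 = 100 mg/mL |
| 8.1.4, possible future vial | 1050 mg in 10.5 mL | 1050 / 10.5 = 100 mg/mL |
| 8.1.2, possible future vial | 1050 mg/mL | 1050 mg/mL |

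- The 1050 mg/mL in 8.1.2 cannot be reproduced from 8.1.4. The ratio is 1050 / 100 = 10.5.
- Content implied by 1050 mg/mL: 10.5 mL × 1050 = 11,025 mg, and a full 15 mL vial would hold 15 × 1050 = 15,750 mg.
- Volume that holds 2100 mg: 2100 / 100 = 21 mL, or 2100 / 1050 = 2 mL.
- If 2 mL were drawn from a 100 mg/mL product, it would hold 2 × 100 = 200 mg.
- Whole vials that make up 2100 mg: 2100 / 700 = 3 of the current vial, or 2100 / 1050 = 2 of a vial that holds 1050 mg in all.

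**Unit of dose**

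| Place | Unit shown for NIS793 |
|---|---|
| Table 2, column heading | mg/m² |
| Table 2, Arm A cell | mg |
| 5.3.1 | mg, described as fixed |
| 5.3.2 | mg |
| 8.1.1, pharmacokinetic text | mg, flat |
| Calendar footnote C | mg |
| Calendar double-asterisk footnote | weight or surface-area changes, NIS793 not exempted |

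To size the conflict, suppose that 2100 is read per square metre. The documents give no body surface area, so the values below are assumptions.

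| Assumed body surface area (m²) | 2100 × area (mg) | Multiple of 2100 mg |
|---|---|---|
| 1.5 | 3150 | 1.5 |
| 1.7 | 3570 | 1.7 |
| 2.0 | 4200 | 2.0 |
| 2.2 | 4620 | 2.2 |

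For context, section 8.1.1 says that 2100 mg was modelled to match exposure at 30 mg/kg, the top of the dose range it reports.

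**The case against.** The strongest reply is that neither slip is likely to reach a patient, and much of this stands.

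The conflict over vial strength does not touch the product in use, on which 8.1.2 and 8.1.4 agree. The larger vial is only something that may come later, and 8.1.2 describes form; it does not instruct preparation. Read literally, 1050 mg/mL would put 15,750 mg in a full 15 mL vial, which is 15,750 / 2100 = 7.5 times the stated 2100 mg. That sits badly with a single-dose product whose overfill is meant to let the entire dose be withdrawn. If whole vials are withdrawn, which is an inference from 8.1.2, the amount given would not depend on the printed concentration. A tenfold error would require someone to pass over the vial label, the Pharmacy Manual and section 8.1.4.

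In Table 2, the other four drug columns repeat mg/m² in their cells. Only the NIS793 cell reads mg, so the table itself signals a different unit, and the other statements of the NIS793 dose are in mg.

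These arguments lower the probability of an error, but they do not remove the contradictions. Table 2 is the defining table and is in force now. The calendar footnote leaves a reader of its heading without a clear exemption for NIS793. The Pharmacy Manual is not among the documents, so it cannot be shown to settle either point.

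**Conclusion.** The point holds as an internal inconsistency in units, with limited but real potential for error. There are two separate conflicts, and they differ in urgency.

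- **Table 2 heading:** it affects current text. A literal reading changes the amount by a factor equal to the patient's body surface area, 1.5 to 2.2 over the assumed range.
- **Future vial:** the two strengths differ 10.5-fold, or 2 mL against 21 mL for 2100 mg. This matters only if the vial is switched.

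A reader might infer that a tenfold underdose or a roughly twofold overdose is likely, or that the exposure tested in Arm A is already compromised. The documents do not support that. The vial in use is described consistently, the Table 2 cell and sections 5.3.1, 5.3.2 and 8.1.1 and calendar footnote C all use mg, and preparation is governed by a manual that was not available for this review. The 200 mg and 3150 to 4620 mg figures show the size of each conflict; they do not predict what will be given.

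No sample size, power or error rate depends on either passage. This review does not say which dose or vial strength is correct.

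**What to change.** - **Now:** reconcile the unit in the NIS793 column heading of Table 2 with its own cell, with section 5.3.1 and with the calendar footnotes. The double-asterisk footnote should say explicitly whether it applies to NIS793. Check that order sets built from Table 2 agree with the reconciled text.
- **Before any vial switch:** reconcile 8.1.2 with 8.1.4 on the content, fill volume and concentration of the new vial, against the product specification and the Pharmacy Manual.

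The cost is two text corrections and a clarifying phrase in the calendar footnote, which can go into the next amendment. The design and analysis do not change.
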